4.3. Tertiary endpoints

Immunogenicity

- Antibody response to component of the candidate vaccine RTS,S/AS01_E (Coad group and Control group):
 - Anti-catalase antibody concentrations and seropositivity at Day 0 and before administration of RTS,S/AS01_E (Month 4) for the Control group and at Day 0 and at one month post Dose 3 of RTS,S/AS01_E (Month 4) for the Coad group.

5. ANALYSIS SETS

5.1. Definition

5.1.1. Enrolled Set

The enrolled set will include all subjects who signed informed consent.

5.1.2. Exposed Set (ES)

The exposed set (ES) will include all subjects who received at least one dose of the study treatment (i.e. receiving at least one dose of study vaccine or Vitamin A). The ES analysis will be performed per treatment actually administered.

5.1.3. Per-Protocol Set for analysis of immunogenicity (PPS for immunogenicity)

The PPS for analysis of immunogenicity will include all evaluable subjects meeting all eligibility criteria, complying with the procedures defined in the protocol, with no elimination criteria during the study. Subjects with incomplete vaccination course or blood sampling performed outside the protocol defined windows will be eliminated.

Note that in order to align to ICH terminology the Total Vaccinated Cohort and the According To Protocol cohort have been renamed Exposed Set (ES) and Per-Protocol Set (PPS) respectively.

5.2. Criteria for eliminating data from Analysis Sets

Elimination codes are used to identify subjects to be eliminated from analysis. Detail is provided below for each set. Time intervals were defined in advance and are stored in the elimination form document (MALARIA-073 (200596) Criteria for Eliminating Subjects from the Analysis (main analysis visit 6) (12-Feb-2017) version 2.5) in eTMF.

5.2.1. Elimination from Exposed Set (ES)

Code 1030 (Study vaccine not administered at all) and code 900 (invalid informed consent or fraud data) will be used for identifying subjects eliminated from ES.

5.2.2. Elimination from Per-protocol analysis Set (PPS)

5.2.2.1. Excluded subjects

A subject will be excluded from the PPS analysis under the following conditions. These apply to the period from Day 0 to Visit 6.

Code	Condition under which the code is used
900	Invalid informed consent or fraud data
1030	Study vaccine not administered at all
1040	Administration of concomitant vaccine(s) forbidden in the protocol
1050	Randomization failure
1070	Vaccination not according to protocol: Incomplete vaccination course before treatment withdrawal. Wrong replacement or study vaccine administered (not compatible with the vaccine regimen associated to the treatment number). Administered study vaccine reported as being the correct one but is not compatible with the vaccine regimen associated to the treatment number.
1080	Vaccine temperature deviation (non GMP use)
1090	Expired vaccine administered
2010	Protocol violation (inclusion/exclusion criteria)
2040	Administration of any medication forbidden by the protocol
2050	Underlying medical condition forbidden by the protocol
2080	Subjects did not comply with vaccination schedule
2090	Subjects did not comply with blood sample schedule
2100	Serological results not available post-vaccination
2120	Obvious incoherence or abnormality or error in data

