^a Study personnel will visit the children on Days 1, 2, 3, 4, 5 and 6 after Vitamin A administration (Visit 2) and after Visit 3 to record solicited general and unsolicited AEs on diary cards.^b Study personnel will visit the children on Days 1, 2, 3, 4, 5, 6, 7, 8, 9, 10, 11, 12, and 13 after vaccination to record solicited and unsolicited AEs on diary cards.^c Collection of solicited local AE for the two injection sites.^d Seizures occurring within 30 days post-vaccination for vaccine doses administered at 6 and 7.5 months of age (Visits 2 and 3) or 42 days post-vaccination for vaccine doses administered at 9 months of age (Visit 4).

Note: The double-line border following Month 4.5 (Visit 6) indicates the analyses which will be performed on all data (i.e. data that are as clean as possible) obtained up to Month 4.5.

* If the investigator believes there is a reasonable reason to do so, screening procedures may only be repeated once.

† Confirmatory serology tests should be performed to identify cases of vaccine failure.

● is used to indicate a study procedure that requires documentation in the individual eCRF.

○ is used to indicate a study procedure that does not require documentation in the individual eCRF.

Table 7 Intervals between study visits (Amended: 09 August 2016)

Study visit	Timing of visit ^a	Allowed interval ^b
Visit 1 (Screening) ^c	1-28 days before Visit 2	-
Visit 2	6 months of age	Child should be 6 ^c months of age
Visit 3	7.5 months of age	Child should be 7 ^d or 8 ^e months of age but respecting a minimum of 4 weeks (28 days) since previous dose (Visit 2)
Visit 4	9 months of age	Child should be 9 ^f months of age but respecting a minimum of 4 weeks (28 days) since previous dose (Visit 3)
Visit 5	4 weeks after Visit 4	Minimum 4 weeks (28 days) - Maximum 6 weeks (42 days)
Visit 6	2 weeks after Visit 5	Minimum 2 weeks (14 days) - Maximum 3 weeks (21 days)
Visit 7	4 weeks after Visit 6	Minimum 4 weeks (28 days) - Maximum 6 weeks (42 days)
Visit 8	4 weeks after Visit 7	Minimum 4 weeks (28 days) - Maximum 6 weeks (42 days)
Visit 9	4 weeks after Visit 8	Minimum 4 weeks (28 days) - Maximum 6 weeks (42 days)
Visit 10	18 months after Visit 4	17 months (516 days) after Visit 4 – 19 months (577 days) after Visit 4
Visit 11	4 weeks after Visit 10	Minimum 4 weeks (28 days) - Maximum 6 weeks (42 days)
Visit 12	17.5 months after Visit 8	17 months (516 days) after Visit 8 – 19 months (577 days) after Visit 8

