- Anti-inflammatory, analgesics, anti-pyretic, and systemic antibiotics administered starting 30 days before and following each dose of study vaccine.
- Any concomitant vaccination administered in the period starting seven days before the first dose of study vaccine and ending at Visit 5 (Month 4).
- Prophylactic medication (i.e. medication administered in the absence of ANY symptom and in anticipation of a reaction to the vaccination).

E.g. an anti-pyretic is considered to be prophylactic when it is given in the absence of fever and any other symptom, to prevent fever from occurring (fever is defined as temperature $\geq 37.5^{\circ}\text{C}/99.5^{\circ}\text{F}$ for oral, axillary or tympanic route, or $\geq 38.0^{\circ}\text{C}/100.4^{\circ}\text{F}$ for rectal route).

- Any concomitant medications/products/vaccines listed in Section 6.7.2.
- Any concomitant medication/product/vaccine relevant to a SAE* or administered at any time during the study period for the treatment of a SAE*.

* SAEs that are required to be reported per protocol.

- Any concomitant medications/products/vaccines relevant to a SAE/pIMD to be reported as per protocol or administered at any time during the study period for the treatment of a SAE/pIMD. In addition, concomitant medications relevant to SAEs and pIMD need to be recorded on the expedited Adverse Event report.

6.7.2. Concomitant medications/products/vaccines that may lead to the elimination of a subject from ATP analyses

The use of the following concomitant medications/products/vaccines will not require withdrawal of the subject from the study but may determine a subject's evaluability in the ATP analysis. See Section 10.5 for cohorts to be analyzed.

- Use of a drug or vaccine that is not approved for that indication (by one of the following regulatory authorities: FDA or European Union member state or WHO [with respect to prequalification]) other than the study vaccines during the study period.
- Immunosuppressants or other immune-modifying drugs administered chronically (i.e. more than 14 days) during the study period. For corticosteroids, this will mean prednisone ≥ 0.5 mg/kg/day or equivalent. Inhaled and topical steroids are allowed.
- A vaccine not foreseen by the study protocol administered during the period starting from seven days before each dose of vaccine(s) and ending 42 days after.*

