10.5.2. According-to-protocol cohort for analysis of immunogenicity (ATP immunogenicity)

The ATP cohort for analysis of immunogenicity will include all evaluable subjects meeting all eligibility criteria, complying with the procedures defined in the protocol, with no elimination criteria during the study. Subjects with incomplete vaccination course or blood sampling performed outside the protocol defined windows will be eliminated.

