10.11. Conduct of analyses

Any deviation(s) or change(s) from the original statistical plan outlined in this protocol will be described and justified in the final study report.

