6.4.2. Additional considerations

Standard data derivation procedures for immunogenicity are available in Section 11 (see Section 11.2.4).

The primary analysis will be based on the PPS cohort for analysis of immunogenicity. If, the percentage of vaccinated subjects with serological results excluded from the PPS cohort for analysis of immunogenicity is 5% or more, a second analysis based on the ES will be performed to complement the PPS analysis.

Statistical methods for Geometric Mean Titres/Concentrations and GMT ratio

Within group assessment

GMTs and GMCs and associated two-sided 95% CIs will be computed for each group and for each strain at each available immunogenicity monitoring (see Section 6.4– Immunogenicity monitoring). The 95% CI for the mean of log-transformed titre (or concentration) will be first obtained assuming that log-transformed titres (or concentrations) are normally distributed with unknown variance. Logarithmic transformations use base 10. The 95% CI for the GMT (or GMC) will then be obtained by exponential transformation (base 10) of the 95% CI for the mean of the log-transformed titres (or concentrations).

Between group assessment

The group GMT ratio (RTS,S group over Coad group) of anti-CS at one month post Dose 3 of RTS,S/AS01_E will be obtained using an ANOVA model on the logarithm-transformed titres. The ANOVA model will include the study group as fixed effect. The GMT ratio and its two-sided 95% CI will be derived as exponential-transformation (base 10) of the corresponding group contrast in the model.

Reverse cumulative distribution curves

Reverse cumulative distribution (RCD) curves for antibody titres will be plotted: the x-axis represents the antibody titres value (log-10 scale), while the y-axis the percentage of subjects having a log-transformed antibody value greater or equal to the corresponding x-value. RCD curves analysis is performed by study group for the following immunogenicity monitoring:

- one month post Dose 3 of RTS,S/AS01E for anti-CS and anti-HBs titres
- one month post-vaccination with the YF vaccine and the combined measles and rubella vaccine for anti-Me, anti-Ru and anti-YF titres

Statistical methods for seropositivity/seroprotection rates and for seroconversion/seropositivity rates differences

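### The per-protocol elimination period runs to Visit 6, 14 to 21 days after the last immunogenicity sample, so as written an event after the draw can remove a valid Month 4 titre; the effect is probably small

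*SAP*

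**What the plan says.** SAP 5.2.2.1 lists the PPS exclusion codes and gives one period for all of them: "These apply to the period from Day 0 to Visit 6". SAP 5.2 adds that "Time intervals were defined in advance and are stored in the elimination form document". That form is not among the documents.

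The breadth starts in the protocol. Section 10.5.2 defines the According-to-Protocol (ATP) cohort as children "complying with the procedures defined in the protocol, with no elimination criteria during the study", and SAP 5.1.3 repeats this for the renamed set. Footnote b of protocol Table 7 makes a child ineligible for that cohort if a study visit falls outside its interval, and does not exempt Visit 6. Protocol 6.7.2 lists what may cost a child its place in the ATP analysis:

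- a vaccine not foreseen by the protocol, given "during the period starting from seven days before each dose of vaccine(s) and ending 42 days after";
- a measles, rubella or yellow fever dose up to the first birthday;
- immunoglobulins or blood products at any time in the study period.

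The primary endpoint (SAP 4.1) is anti-CS at Month 4. The sampling schedule in protocol Section 3 ends at Month 4 (Visit 5) in all three arms.

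**The concern.** A per-protocol immunogenicity set should exclude children whose titre may not reflect the planned regimen. An event after the blood is drawn cannot change the titre in the tube, so excluding the child discards valid data for no gain. The primary conclusion rests on this set.

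The second issue is balance. At Visit 6 the RTS,S arm is due its yellow fever and measles-rubella vaccines and the Control arm its first RTS,S/AS01_E dose, while Coad is due nothing. If Visit 6 is inside the period, dose-linked exclusions after the sample can fall only on the comparator arms. That touches the primary contrast (RTS,S over Coad) and the secondary contrasts (Control minus Coad), in an open-label trial.

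**Working it through.** **1. The gap.** Inputs from protocol Table 7: Visit 5 is 28 to 42 days after Visit 4, and Visit 6 is 14 to 21 days after Visit 5. Visit 6 is therefore 28 + 14 = 42 to 42 + 21 = 63 days after Visit 4. The last 14 to 21 days of the elimination period follow the last sample.

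**2. Which codes can newly arise in that gap.** Codes are from SAP 5.2.2.1 and Annex 2; Visit 6 doses are from protocol Table 12.

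| Codes | Can a post-sample event trigger them? | Arms |
|---|---|---|
| 900, 1030, 1050, 2010 | No; they concern consent or fraud, never being vaccinated, randomisation and entry criteria | none |
| 2090 | No; settled at the draw | none |
| 2100, 2120 | Yes, but they bear on whether a valid result exists | Any |
| 1040 (forbidden vaccine) | Yes | Any |
| 2040, 2050 (medication, medical condition) | Yes | Any |
| 1070, 1080, 1090, 2080 (dose-linked) | Only through a Visit 6 dose, if Visit 6 counts | RTS,S and Control only |

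For code 1040, the 42-day window after the Visit 4 dose leaves 42 - 42 = 0 to 42 - 28 = 14 days after the sample. The separate limit on outside measles, rubella or yellow fever vaccine runs to the first birthday, which is still ahead at the planned Visit 6 age of 10.5 months. The blood-product rule has no end date within the study.

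**3. The plan's own figures (protocol 10.4).** 233 x 0.12 = 28, and 233 - 28 = 205 evaluable per arm. For anti-CS, reading the SD of 0.9 as log10:

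Power = Phi( log10(2) / (0.9 x sqrt(1/n1 + 1/n2)) - 1.96 )

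With n1 = n2 = 205: 0.3010/0.0889 = 3.386; 3.386 - 1.96 = 1.426; Phi = 92.3%. This agrees with the stated minimum of 90%.

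**4. Effect on power.** Losses inside the 12% allowance cost no planned power. Losses beyond it, in the RTS,S arm only (Coad at 205):

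| RTS,S n | Lost beyond allowance | z | Power |
|---|---|---|---|
| 205 | 0 | 1.426 | 92.3% |
| 200 | 5 | 1.405 | 92.0% |
| 174 | 31 | 1.285 | 90.06% |
| 173 | 32 | 1.280 | 89.97% |

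For rubella and measles seroconversion (90% in both arms, margin 10%), score-test power is Phi((0.10 - 1.96 x s0)/s1). Here s1 = sqrt(2 x 0.9 x 0.1/n), and s0 is the standard error from the maximum-likelihood rates restricted to a difference of 0.10 (0.831 and 0.931). At 205 per arm, s0 = 0.0316, s1 = 0.0296 and power is 90.1%, matching the stated 90%. At 200 per arm, s0 = 0.0320, s1 = 0.0300 and power is 89.4%.

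**5. Effect on the ratio.** If exclusion is unrelated to titre, the expected shift is zero. Assume instead that 5 of 205 RTS,S children are removed and differ from the arm mean by 0.3 log10. The GMT ratio is then multiplied by 10^(±0.3 x 5/205), that is 0.98 to 1.02, against a margin of 2. Both the 5 and the 0.3 are illustrative; neither comes from the documents.

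**The case against.** The strongest reply is that the operative rule is out of sight. SAP 5.2 places the time intervals in the elimination form, whose title refers to the main analysis at Visit 6. The phrase in 5.2.2.1 may simply name the data cut for that analysis, with narrower windows by code held in the form. This stands as a limit on what can be concluded about practice. It does not remove the point, because 5.2.2.1 states a period and nothing in the SAP confines any code to events before the sample.

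The routes are also fewer than the code list suggests. Code 1040 has at most 14 post-sample days from the Visit 4 dose, and an immunosuppressant counts only after more than 14 days of use, so a course begun after Visit 5 could barely qualify. The outside measles, rubella or yellow fever dose and the blood product remain.

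SAP 6.4.2 offers a partial safeguard: if the share of vaccinated subjects with serology who are "excluded from the PPS cohort for analysis of immunogenicity is 5% or more, a second analysis based on the ES will be performed". That analysis is conditional and complementary, and does not replace the PPS result.

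Four stronger readings are tempting, and the documents do not support them:

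- *The SAP breaches the protocol.* The protocol's own definition is open-ended; the SAP's limit at Visit 6 is narrower.
- *SAP 5.1.3 and 5.2.2.1 contradict each other.* The wording in 5.1.3, "with no elimination criteria during the study. Subjects with incomplete vaccination course", is a general definition taken from the protocol, and 5.2.2.1 gives its operational detail.
- *A Coad child with an out-of-window Visit 6 is removed.* Table 7 footnote b could be read so, but no SAP code does this. Codes 2080 and 2090 concern doses and samples, and Coad has neither at Visit 6.
- *The 12% allowance, spread over calendar time, gives a count of children lost.* Many codes cluster at entry, doses and samples, and the allowance also covers drop-outs, so such a count has no basis.

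**Conclusion.** The point holds as a minor one. The stated elimination period outlasts the last sample by 14 to 21 days, and at least two routes (an outside measles, rubella or yellow fever dose, and a blood product) can remove a valid Month 4 titre in any arm. Whether exclusions can also be arm-dependent turns on whether Visit 6 is inside the period, which the SAP leaves open. If it is, the dose-linked codes at that visit reach only the two comparator arms.

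The size is not documented and is probably small. Five RTS,S children lost beyond the allowance cost 0.3 points of anti-CS power, and 32 would be needed to fall below 90%. Rubella and measles have less room, at 90.1% with 205 per arm. These figures rest on a log10 SD of 0.9 and no true difference between arms. The direction of any bias is unknown, because nothing links these deviations to titre. The conclusion concerns the rule as written; the elimination form may already be narrower.

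**What to change.** In SAP 5.2.2.1, for the immunogenicity PPS:

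- State that codes 1040, 1070, 1080, 1090, 2040, 2050 and 2080 apply to deviations occurring from Day 0 up to the Visit 5 blood sample, whenever they are discovered.
- State that Visit 6 dose or interval deviations do not eliminate a child from this set.
- Leave codes 900, 1030, 1050, 2010, 2090, 2100 and 2120 unchanged. Laboratory, labelling and data errors can arise after the draw and must still eliminate.

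Word SAP 5.1.3 to match, and align the elimination form named in SAP 5.2. Record in SAP Section 9 the departure from protocol Table 7 footnote b, 6.7.2 and 10.5.2, and justify it in the study report, since protocol 10.11 requires that "Any deviation(s) or change(s) from the original statistical plan outlined in this protocol will be described and justified in the final study report".

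The cost is a few sentences, a new version of the form, and a documented departure from the protocol's ATP definition, which is the main downside. No new data are needed.

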5.7.4. Biological samples evaluation

5.7.4.1. Immunological read-outs

Blood samples will be collected for assessment of serology.

Table 10 Immunological read-outs

Blood sampling timepoint		study group	No. subjects	Component	Components priority rank
Type of contact and timepoint	Sampling timepoint				
Visit 2	Day 0	Coad group and RTS,S group	466	anti-CS	1
		Coad group and RTS,S group	466	anti-HBs	2
		Coad group and Control group	466	anti-catalase	3
Visit 4	Month 3	Coad group and Control group	466	anti-Me	1
		Coad group and Control group	466	anti-Ru	2
Visit 5	Month 4	Coad group and RTS,S group	466	anti-CS	1
		Coad group and RTS,S group	466	anti-HBs	5
		Coad group and Control group	466	anti-catalase	6
		Coad group and Control group	466	anti-Me	2
		Coad group and Control group	466	anti-Ru	3
		Coad group and Control group	466	anti-YF	4

In case of insufficient blood sample volume to perform assays for all antibodies, the samples will be analyzed according to priority ranking provided in [Table 10](#).

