10.4. Determination of sample size

For the primary endpoint, with 205 evaluable subjects per group the study has at least 90% power to rule out a minimum 2-fold decrease in anti-CS GMTs in the Coad group versus the RTS,S group with a 2-sided 5% alpha level and an assumed anti-CS log standard deviation of ≤ 0.9 (see [Table 19](#)).

For the secondary endpoints, the power to demonstrate non-inferiority in terms of anti-YF, anti-Ru and anti-Me with 205 evaluable subjects per group is presented in [Table 19](#). Non-inferiority is defined as the UL of the 95% CI on the difference (Control group minus Coad group) in response $<10\%$.

In order to account for drop-outs and subjects non-evaluable for immunogenicity endpoints (approximately 12%), 233 subjects per group will be enrolled for a total of 699 subjects.

Table 19 Sample size and power

Antibody	Endpoint	Non-inferiority limit	Reference in control	Power
Anti-CS	GMT ratio (RTS,S group / Coad group)	2-fold decrease	log SD ≤ 0.9	90%
Anti-Ru	Seroconversion	10%	90%*	90%
Anti-YF	Seropositivity	10%	95%**	99%
Anti-Me	Seroconversion	10%	90%**	90%

Power of a non-inferiority test on seroconversion/positivity or means, 2-sided alpha 0.05, N=205 (Pass 2005).

* Adapted from Rubella vaccines: WHO position paper [[WHO](#), 2011].

** [[GlaxoSmithKline Biologicals Clinical Study Report Amendment 1 - 106369](#) (MALARIA-050)].

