11.2.4. Immunogenicity

- For a given subject and given immunogenicity measurement, missing or non-evaluable measurements will not be replaced. Therefore, an analysis will exclude subjects with missing or non-evaluable measurements.
- The Geometric Mean Concentrations/Titres (GMC/Ts) calculations are performed by taking the anti-log of the mean of the log titre transformations (base 10). Antibody titres below the cut-off of the assay will be given an arbitrary value of half the cut-off of the assay for the purpose of GMT calculation. The cut-off value is defined by the laboratory before the analysis.
- A subject seropositive for anti-CS antibody will be a subject whose antibody titre will be greater than or equal to the cut-off value (anti-CS \geq 1.9 EU/ml).
- A subject seropositive for anti-HBs antibody will be a subject whose antibody titre will be greater than or equal to the cut-off value (anti-HBs \geq 6.2 mIU/ml).
- Seroprotection rate for anti-HBs antibody is defined as the percentage of subjects with antibody titres greater than or equal to 10 mIU/ml (anti-HBs \geq 10 mIU/ml).

- Seroconversion rate for anti-Me is defined as the percentage of children with an anti-Me pre-vaccination titre below 150 mIU/ml and a post-vaccination titre \geq 150 mIU/ml (i.e. the subject is seropositive post-vaccination and seronegative pre-vaccination for anti-Me).
- Seroconversion rate for anti-Ru is defined as the percentage of children with an anti-Ru pre-vaccination titre below 4 IU/ml and a post-vaccination titre \geq 4 IU/ml (i.e. the subject is seropositive post-vaccination and seronegative pre-vaccination for anti-Ru).
- Seroprotection rate for anti-Ru antibody is defined as the percentage of subjects with antibody titres greater than or equal to 10 IU/ml (anti-Ru \geq 10 IU/ml).
- A subject seropositive for anti-YF antibody will be a subject whose antibody titre will be greater than or equal to the cut-off value (anti-YF \geq 10 ED50).
- A subject seropositive for anti-catalase antibody will be a subject whose antibody concentration is greater than or equal to 65 ng/ml.
- The assay cut-off is the value under which there is no quantifiable result available. For an assay with a specific 'cut_off' , numerical immuno result is derived from a character field (rawres):
 - If rawres is 'NEG' or '-' or '(-)', numeric result= cutt_off/2,
 - if rawres is 'POS' or '+' or '(+)', numeric result = cut_off,

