12. ANNEX 2: SUMMARY ON ELIMINATION CODES

Table 6 Safety Sets

PD code	PD Description	Study Objective/ Period	All Exposed Set
		Exclusion code	EXPFL
1030	Study vaccine not administered AT ALL	All Study	EXC
900	Invalid inform consent or fraud data		EXC

EXC = excluded from this analysis set.

Table 7 Immunogenicity Sets

PD code	PD Description	Study Objective/ Period	All Exposed	PPS
		Exclusion code	EXPFL	PPSFL
1030	Study vaccine not administered AT ALL	All Study	EXC	EXC
900	Invalid inform consent or fraud data		EXC	EXC
1040	Administration of forbidden vaccine			EXC
1050	Randomization failure			EXC
1070	Wrong replacement of study vaccine administered			EXC
1070	Administered study vaccine reported as correct but not compatible with regimen associated to treatment number			EXC
1070	Incomplete vaccination course			EXC
1080	Administration of temperature-deviated vaccine			EXC
1090	Administration of expired vaccine			EXC
2010	Subject did not meet entry criteria			EXC
2040	Administration of forbidden medication			EXC
2050	Underlying medical condition forbidden by the protocol			EXC

CONFIDENTIAL200596 (MALARIA-073)
Statistical Analysis Plan Final

PD code	PD Description	Study Objective/ Period	All Exposed	PPS
			EXPFL	PPSFL
2080	Did not comply with study vaccination schedule			EXC
2090	Did not comply with blood draw schedule			EXC
2100	Serological results are not available			EXC
2120	Obvious deviation from Laboratory Manual or error in laboratory data			EXC
2120	Incoherence between CRF and CLS database in terms of sample availability (e.g. sample not collected but result is available)			EXC
2120	Label error of blood samples that could not be resolved			EXC

PPS=Per Protocol Set; EXC = excluded from this analysis set

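### One subject-level Per-Protocol flag serves every antigen, so a Coad child with a valid Month 4 anti-CS titre can be excluded over a sample or result that RTS,S children never have (minor)

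*SAP*

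**What the plan says.** SAP 5.1.3 defines one PPS for immunogenicity, and SAP 6.4.1 bases the primary anti-CS comparison on it. SAP 5.1.3 adds that subjects with an incomplete vaccination course or "blood sampling performed outside the protocol defined windows will be eliminated".

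SAP 5.2.2.1 excludes the subject, over the period from Day 0 to Visit 6, under a list of codes. Three concern samples and results:

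- **Code 2090:** "Subjects did not comply with blood sample schedule".
- **Code 2100:** no serological result after vaccination. Annex 2 Table 7 words it more widely: "Serological results are not available".
- **Code 2120:** incoherent or erroneous data. Annex 2 Table 7 includes unresolved label errors on blood samples and disagreement between the CRF and the laboratory database over whether a sample exists.

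Table 7 has one PPS column, covering every antigen. Mock Template 9 describes code 2100 as missing *essential* serological data but does not define the word.

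Two other rules work at the level of the single result. SAP 11.2.4 does not replace missing results and continues: "Therefore, an analysis will exclude subjects with missing or non-evaluable measurements". Protocol 5.7.4.1 says: "In case of insufficient blood sample volume to perform assays for all antibodies, the samples will be analyzed according to priority ranking". Its Table 10 ranks anti-CS first at Month 4.

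**The concern.** The primary test needs one result per child, the Month 4 anti-CS titre. The two arms it compares do not have the same samples. A Coad child has a Month 3 measles/rubella draw and Month 4 measles, rubella, yellow fever and catalase assays; an RTS,S child has none of these. With one flag for all antigens, a fault in one of those extra samples or results can take a valid anti-CS titre out of the primary analysis in Coad, and no such fault can occur in RTS,S.

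At stake is some valid primary-endpoint data and, if the faults are related to anti-CS titre, a selection that differs by arm. It also sits badly with the plan's own rules: Table 10 protects anti-CS in a short sample, and a literal code 2100 would then discard the child whose anti-CS result had been protected. The same flag governs the Control versus Coad tests, where a Day 0 sample problem unrelated to measles, rubella or yellow fever could have the same effect.

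**Working it through.** **Planned results per child** (Protocol Table 10):

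| Group | Day 0 | Month 3 | Month 4 | Total |
|---|---|---|---|---|
| Coad | 3 | 2 | 6 | 11 |
| RTS,S | 2 | 0 | 2 | 4 |
| Control | 1 | 2 | 4 | 7 |

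Seven Coad results have no RTS,S counterpart: Day 0 catalase, Month 3 measles and rubella, and Month 4 measles, rubella, yellow fever and catalase.

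**The plan's own figure.** Protocol 10.4 states that "with 205 evaluable subjects per group the study has at least 90% power", "with a 2-sided 5% alpha level and an assumed anti-CS log standard deviation of" at most 0.9. The log is base 10 (Protocol 10.6), the margin is log10(2) = 0.301, and a true ratio of 1 is assumed, since none is stated. The standard error is 0.9 × √(2/205) = 0.0889. Power = Φ(0.301/0.0889 − 1.96) = 92.3% (92.2% with the non-central t), which meets the stated minimum. Enrolment is 205/0.88 = 233. Both reproduce.

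**Code by code.**

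- *2090.* The Month 3 draw is taken at Visit 4, and Protocol Table 7 sets one Visit 4 window for all arms. A late Visit 4 excludes an RTS,S child too.
- *2120.* An unresolved label error on the Month 3 measles/rubella sample excludes a Coad child from the anti-CS analysis. RTS,S children have no Month 3 sample. This follows from the text without further assumption; the documents give no rate for it.
- *2100.* The effect depends on the reading. If any missing Month 4 result counts, the calculation below applies. If only the result being analysed counts, there is no effect.

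**Size under the wide reading of 2100.** Assume each Month 4 result is independently missing with probability q. The documents give no rate; 1% is an assumption, with range 0.5% to 2%. Among children whose anti-CS result is available, the proportion excluded is 1 − (1 − q)^5 in Coad (five other results) and 1 − (1 − q)^1 in RTS,S (anti-HBs only). Power is recomputed with both arms reduced from 205 and the loss unrelated to titre.

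| q | Coad | RTS,S | Remaining Coad / RTS,S | Power |
|---|---|---|---|---|
| 0.5% | 2.5% | 0.5% | 200 / 204 | 91.9% |
| 1% | 4.9% | 1.0% | 195 / 203 | 91.5% |
| 2% | 9.6% | 2.0% | 185 / 201 | 90.7% |

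For q = 1% the standard error is 0.9 × √(1/195 + 1/203) = 0.0903, and Φ(0.301/0.0903 − 1.96) = 91.5%. If only Coad lost children, power would fall below 90% at 173 or fewer in Coad.

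**Bias, if loss is related to titre.** Suppose excluded children in both arms have titres d log10 lower than retained ones (assumed). At q = 1% the net shift in the log10 ratio is (0.049 − 0.010) × d.

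- d = 0.2: shift 0.0078, ratio understated by a factor of 10^0.0078 = 1.018; one-sided type I error at a true ratio of 2 is 1 − Φ(1.96 − 0.0078/0.0903) = 3.0% instead of 2.5%.
- d = 0.6: shift 0.0234, factor 1.055, type I error 4.5%.
- Titres higher by the same amounts: power Φ((0.301 − shift)/0.0903 − 1.96) = 90.1% and 86.8%.
- d = 0: no bias.

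**The back-up analysis.** SAP 6.4.2 adds an analysis on the Exposed Set if 5% or more of vaccinated subjects with serological results are excluded from the PPS. At q = 1%, the proportion with any Month 4 result missing is 1 − 0.99^6 = 5.9% in Coad, 1 − 0.99^2 = 2.0% in RTS,S and 1 − 0.99^4 = 3.9% in Control, an average of 3.9%. This route alone would not reach an overall 5% although Coad exceeds it. Other exclusions could still trigger it.

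**The case against.** A reader might infer that valid primary data will be lost, mostly in Coad, and that the non-inferiority conclusion will rest on an arm-dependent selection. The documents do not support that, for these reasons:

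- **Code 2100 has a narrower reading.** Template 9 speaks of essential data, SAP 11.2.4 works per measurement, and Templates 13 to 22 count subjects with available results. If any missing Month 4 assay removed the child, much of this would be redundant within the PPS. This stands. It leaves an undefined term, and the mock tables are described as illustrative.
- **Short serum is less likely in Coad than it looks.** The Month 4 minimum volumes sum to 1.2 + 0.6 + 0.6 + 0.6 = 3.0 ml, while Protocol Table 8 collects 3.5 ml. RTS,S (1.2 ml) and Control (1.8 ml) collect exactly their minimum. This stands.
- **The asymmetry is not all one way.** The codes run to Visit 6, when RTS,S children receive the yellow fever and measles/rubella vaccines, so vaccination codes could remove an RTS,S child with a valid titre. This stands as a separate matter.
- **Safeguards exist.** The Exposed Set drops subjects only for codes 900 and 1030, so that analysis would restore these titres, and Template 9 shows exclusions by code and arm. This stands in part: the Exposed Set analysis is complementary and conditional, and its trigger is not stated per arm or per antigen.
- **The elimination form may already restrict the codes.** SAP 5.2 cites it for time intervals and it cannot be seen here. If it does so, one sentence in the SAP would settle the point.

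None of this answers code 2120, or the absence of any text limiting a code to the antigen analysed.

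**Conclusion.** The point holds as a minor one. The single flag allows a Coad child with a valid Month 4 anti-CS titre to leave the primary analysis because of a sample or result that RTS,S children do not have. This is clear for code 2120, depends on the reading for code 2100, and is negligible for code 2090.

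The size is unknown and probably small. The excess of about 4.9% against 1.0% rests on an assumed 1% independent failure rate and the wide reading of code 2100; failures that cluster within a child would make it smaller. A reader might also infer a threat to power or a known bias. Power stays above 90% over the assumed range when loss is unrelated to titre. No passage links a missing measles, rubella, yellow fever or catalase result to anti-CS titre, so the bias figures show only what would follow if such a link existed.

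**What to change.** In SAP 5.2.2.1 and Annex 2 Table 7, apply codes 2090, 2100 and 2120 per antigen and only to the samples that the analysis needs:

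- primary test: Month 4 anti-CS;
- anti-HBs: Month 4;
- anti-measles and anti-rubella: Month 3 and Month 4, each antigen separately;
- anti-yellow fever: Month 4.

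Define *essential* in code 2100 in the same terms. Leave the eligibility, vaccination and forbidden-medication codes as they are.

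The cost is a few lines of text and antigen-specific flags in Table 7 in place of the single column. The number analysed will differ by antigen, which SAP 11.2.4 already implies.
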